### 5.2.3 Follow-up Period

Study Procedure	Follow-up Period	Unscheduled Visit  (if applicable)	Early Termination (if applicable)
Visit (V)	V34		
Week (W)	W36		
Day (D)	D252		
Visit Window (d)	±3d		
Treatment:			
Con Meds/Treatments	X	X	X
Efficacy:			
IGA, EASI, GISS, SCORAD, BSA	X	X	X
POEM, DLQI, HADS	X	X	X
Patient Diary (daily)		X	X
Safety:			
Vital Signs	X	X	X
Physical Examination	X	X	X
Electrocardiogram		X	
Adverse Events	X	X	X
Laboratory Testing:			
Hematology, Chemistry, Inflammation Markers	X	X	X
Infectious Disease Panel		X	
Urinalysis	X	X	X
Pregnancy Test (WOCBP only)	Urine	Urine/Serum	Serum
PK/PD/ADA:			
PK/ADA, IL-6, PD, biomarker & research samples (serum/plasma)	X	X	X
 Assessments/procedures should be conducted in the following order: patient assessments, investigator assessments, safety and laboratory assignments			
 During an unscheduled visit, any of the study procedures noted may be performed, but not all are required.			

### **5.3 DISCONTINUATION OF THERAPY**

If a patient is discontinued from study, the reason for discontinuation/withdrawal must be clearly documented in the source documentation and the EDC. Every effort should be made by the investigative site to have subjects who discontinue early from study complete all assessments included in the Early Termination visit included in the study calendar provided in section 5. All subjects will be unblinded after clinical database lock.

Study therapy **MUST** immediately be discontinued for any the following reasons:

- Withdrawal of informed consent (subject's decision to withdraw for any reason)
- Any clinical adverse event, laboratory abnormality, inter-current illness, or clinical progression of disease which, in the opinion of the Principal Investigator, indicates that continued participation in the study is not in the best interest of the subject
- Pregnancy
- Termination of the study by the sponsor
- Imprisonment or the compulsory detention for medical treatment.

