## **2.10 PROHIBITED MEDICATIONS AND PROCEDURES**

Treatment with the following concomitant medications is *prohibited* during the entire duration of the study:

- Topical tacrolimus and pimecrolimus
- Treatment with a live (attenuated) vaccine
- Treatment with other investigational drugs (besides Bermekimab)
- Treatment with topical corticosteroids or topical calcineurin inhibitors; such agents may be administered during the study only if required for atopic dermatitis rescue. If topical corticosteroids and/or topical calcineurin inhibitors are used during the study, study treatment may continue as planned.
- Treatment with systemic corticosteroids or nonsteroidal systemic immunosuppressive drugs (e.g., cyclosporine, methotrexate, mycophenolate-mofetil, azathioprine, etc.), except if required for atopic dermatitis rescue, or if critically medically needed to treat concurrent medical conditions (e.g., asthma).
  - The use of systemic corticosteroids for indications other than AD should be limited to situations for which, in the opinion of the treating physician, there are no adequate alternatives. They should be used on a short-term basis, preferably for  $\leq 2$  weeks. Longer-term use of corticosteroids should be discussed with the medical monitor or designee and may require discontinuation of study drug. Inhaled, otic, ocular, nasal or other routes of mucosal delivery of corticosteroids are allowed throughout the study.
- Leukotriene inhibitors

- Allergen immunotherapy
- Systemic treatment for AD with an immunosuppressive/immunomodulating substance (including, but not limited to, cyclosporine, mycophenolate-mofetil, IFN- $\gamma$ , azathioprine, methotrexate, or biologics)

Study drug will be discontinued if any of the following are used through week 16:

- Treatment with a live (attenuated) vaccine
- Treatment with investigational drugs other than bermekimab.
- Treatment with systemic corticosteroids or nonsteroidal systemic immunosuppressive drugs (e.g., cyclosporine, methotrexate, mycophenolate-mofetil, azathioprine, etc.)

The following concomitant procedures are prohibited during study participation:

- Surgical procedures
- Concomitant ultraviolet (UV) procedures (phototherapy [NBUVB, UVB, UVA1, or PUVA])
- Tanning in a bed/booth
- Patients are not allowed more than 2 bleach baths per week during study participation

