In the event of an emergency that would require the investigator to be aware of the treatment allocation prior to the end of the trial, the investigator can obtain this information, on a per subject basis, after consultation with the Sponsor's Medical Monitor, if possible. Every effort should be made to consult with the Medical Monitor prior to emergency unblinding. Events that qualify as emergencies are as follows:

- A grade 3 or greater AE which are “probably or definitely” related to study drug, and only if treatment assignment information is essential for the management of the event. This type of reaction would require that the patient receives no further doses and is followed until the resolution of the toxicity.
- Any suspected, unexpected, serious adverse reaction (SUSAR)
- Pregnancy

The investigator may, in an emergency, determine the identity of the intervention through the EDC system. While the responsibility to break the intervention code in emergency situations resides solely with the investigator, it is recommended that the investigator contact the sponsor or its designee if possible, to discuss the particular situation, before breaking the blind. Telephone contact with the sponsor or its designee will be available 24 hours per day, 7 days per week. In the event the blind is broken, the sponsor must be informed as soon as possible. The date and reason for unblinding must be documented in the appropriate section of the eCRF, and in the source document.

Participants who have had their intervention assignment unblinded by the investigator will not be eligible to receive further study intervention but should continue to complete evaluations specified in the Study Calendars (Section 5.2 of the protocol).

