## **2.2. Visit Windows**

Nominal visits will be used for all by-visit analyses in the study. The study visits scheduled post randomization should occur at the times delineated in the Schedule of Activities. The study visits through Week 36 should occur within  $\pm 3$  days of the scheduled visit. The sponsor must be contacted for any significant deviation in the scheduling of a visit outside the appropriate window and determine how the subject should resume his/her normal dosing schedule relative to the baseline visit (Week 0).

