### **5.2.2. Data Handling Rules**

No imputation will be performed for missing baseline values.

For the main analysis of primary endpoint of EASI-75 response at Week 16, a subject who discontinued treatment will be considered as a non-responder from that point onward. The remaining missing data will be imputed as non-responder. Supplementary analyses will be performed and include (1) using observed data regardless of whether the subject discontinued treatment or have missing data, and (2) data after treatment discontinuation will be considered as missing, missing response will be imputed by multiple imputation methods under the assumption of missing at random. Similar data handling rules (i.e., main analysis with non-responder imputation and 2 supplementary analyses) will also be applied for EASI-75 response over time through Week 16. The following data handling rules will be applied for other endpoints:

Binary secondary endpoints:

- Analyses will be similar to the main analysis of the primary endpoint. A subject who discontinued treatment will be considered as a non-responder from that point onward. The remaining missing data will be imputed as non-responder. Supplementary analyses will be performed for selected endpoint (i.e IGA responses) in the same manner as the primary endpoint.

Continuous secondary endpoints:

- If a subject discontinued treatment, zero will be assigned to improvement or percent improvement. Remaining missing data will not be imputed. A MMRM model will adjust for missing post baseline data and all available data from the 3 treatment groups through Week 16 or from Week 16 through Week 36 will be included. Under the assumption of missing at random (MAR), the missing data will be accounted for through correlation of repeated measures in the model. Supplementary analyses will be performed for selected endpoints (i.e. EASI total score, NRS itch score) and include (1) using observed data regardless of whether the subject discontinued treatment or have missing data, and (2) data after treatment discontinuation will be considered as missing, missing data will be addressed by MMRM model.

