#### Supplementary Estimands for primary endpoint:

##### Supplementary Estimand 1

Same components as the primary estimand, except for the strategy used for treatment discontinuation.

**Hypothetical strategy:** assess the treatment effect as if the participants would not have discontinued treatment.

Note: Under this hypothetical strategy, EASI data collected after treatment discontinuation will not be used and will be set to missing in analysis.

##### Supplementary Estimand 2

Same components as the primary estimand, except for the strategy used for treatment discontinuation.

**Treatment policy strategy:** assess the treatment effect regardless of treatment discontinuation.

Note: Under the treatment policy strategy, EASI data collected after treatment discontinuation will also be used in analysis.

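### Protocol 5.3 does not separate stopping study drug from leaving the study, so the off-drug assessments behind the SAP's treatment-policy analyses are not required of sites

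*Protocol*

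**What the plan says.** **Protocol.** Section 5.3 carries a heading about therapy, but its visit sentence concerns the study: sites are to try to have "subjects who discontinue early from study complete all assessments included in the Early Termination visit". A documented reason is asked for when a patient is discontinued from study. One of its five grounds for stopping therapy is an event or illness that in the investigator's opinion "indicates that continued participation in the study is not in the best interest of the subject". Section 2.10 describes stopping drug alone ("Study drug will be discontinued if any of the following are used through week 16") and is silent on later visits. The Early Termination visit collects EASI, IGA and the diary, but the calendar in 5.2.3 gives it no week number.

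**SAP.** Section 5.2.2 plans two supplementary analyses, of which the first is described as "using observed data regardless of whether the subject discontinued treatment or have missing data, and (2) data after treatment discontinuation will be considered as missing". They apply to EASI-75 and IGA response, and to EASI total score and itch NRS. Under the treatment-policy estimand in 5.3.2, "EASI data collected after treatment discontinuation will also be used in analysis". Sections 5.3.5, 5.4.2.2, 5.4.3.2 and 5.4.4.2 carry these analyses out. Section 2.2 states that "Nominal visits will be used for all by-visit analyses in the study".

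**Off-drug follow-up is mentioned twice.** SAP 1.5.2 says that patients unblinded by the investigator "will not be eligible to receive further study intervention but should continue to complete evaluations specified in the Study Calendars". The COVID-19 appendix says that follow-up continues after drug is stopped for safety, without saying what is assessed.

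**The concern.** A treatment-policy analysis is only as good as the data collected after treatment stops. Here the SAP defines analyses on off-drug data, while the protocol, which is what sites follow, does not ask for those data in general. A site could reasonably handle a patient who stops injections as a patient leaving the study: one Early Termination visit, then nothing. Values not collected cannot be recovered by an analysis rule.

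The two notions are blurred elsewhere too. Protocol 10.5.3.1 imputes non-response for patients who leave the study before Week 16, whereas SAP 5.3.3 does so for patients who stop treatment. SAP 4.2 tabulates study discontinuation only, although stopping treatment is the intercurrent event of the primary estimand. The protocol's safety endpoint concerns adverse events that lead to stopping treatment; SAP 6.1 summarises those that lead to stopping the study.

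At stake is whether the supplementary analyses can show how far the result depends on the handling of patients who stop drug.

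**Working it through.** **1. The plan's own figure, and what it does not give.** Protocol 10.1 assumes EASI-75 rates of 60% and 20%, two-sided alpha 0.05, about 80% power. With pooled variance, n per arm = [1.96·√(2·0.4·0.6) + 0.8416·√(0.6·0.4 + 0.2·0.8)]² / 0.4² = (1.358 + 0.532)² / 0.16 = 22.3, so 23 per arm and 69 in total; power at 23 is 0.812. The figure is reproduced. Enrolling 90 leaves (90 − 69)/90 = 23.3%, but the protocol assigns that margin to dropouts and safety data together. It is not a rate of stopping drug. I use 10% to 30% around it as an assumed range.

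**2. EASI score and itch.** Analysis (1) uses on-drug and off-drug records; analysis (2) uses on-drug records only. With no off-drug record at a nominal visit, the two record sets coincide. The estimates are then identical if analysis (1) is also an MMRM (implied by SAP 5.1 and 5.4, not stated for that analysis) and if Early Termination values are not assigned to a week (the SAP has no rule).

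A simulation shows how quickly this changes with retention. Its assumptions are not in the documents: 30 per arm; EASI at Weeks 1, 2, 4, 6, 8, 12 and 16; mean improvement levelling off at 14 (weekly), 11 (every other week) and 6 (placebo); SD 9; drug effect lost once drug stops; stopping unrelated to outcome; maximum-likelihood repeated-measures model with unstructured covariance; 25 runs per setting. Mean absolute gap between (1) and (2) in the Week 16 weekly-minus-placebo difference, in EASI points:

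| Stop drug | None retained | 10% retained | 25% retained | All retained |
|---|---|---|---|---|
| 10% | 0.00 | 0.12 | 0.33 | 0.82 |
| 23.3% | 0.00 | 0.33 | 0.59 | 1.95 |
| 30% | 0.00 | 0.40 | 0.69 | 2.18 |

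At 23.3% stopping with none retained, both analyses average 7.34. With all retained they average 5.46 and 7.34. That contrast is what the pair is meant to show.

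**3. EASI-75, treatment policy.** SAP 5.3.5 uses observed values and leaves missing ones unimputed. Let s be the share stopping in each arm and d the active-minus-placebo difference in off-drug response at Week 16. Keep 60% and 20% as the rates with stoppers counted as failures.

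- Treatment-policy difference with all stoppers observed: 0.40 + s·d.
- Difference among patients with data when no stopper is observed: 0.40/(1 − s).

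Taking off-drug response as 20% (active) and 10% (placebo), so d = 0.10:

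- s = 10%: 0.410 against 0.444.
- s = 23.3%: 0.423 against 0.522.
- s = 30%: 0.430 against 0.571.

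At s = 23.3% the gap is 0.122 if d = 0 and 0.028 if d = 0.40. All of these inputs except 60% and 20% are assumptions.

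**4. EASI-75, the pair.** The hypothetical analysis uses multiple imputation and the treatment-policy analysis uses observed cases, so the two remain different even with no off-drug data. In 2,000 simulated trials per setting (30 per arm, on-drug rates 60% and 20%, an earlier response agreeing 85% of the time, a simple conditional imputation standing in for multiple imputation), the observed-case and imputed differences were:

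- 10% stopping: 0.397 and 0.395.
- 23.3% stopping: 0.398 and 0.393.
- Stopping in 35% of early non-responders and 8% of early responders: 0.415 and 0.396.

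The mean absolute gap was 0.02 to 0.04.

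**5. The main analyses.** SAP 5.3.3 counts a patient who stops treatment before Week 16 as a non-responder. SAP 5.2.2 assigns zero improvement in the main continuous analyses. Neither uses an off-drug assessment.

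**The case against.** The sentence in 5.3 is about leaving the study. It does not say that a patient who only stops injections gets only the Early Termination visit, and no text releases such a patient from the calendars in 5.2. The documents do distinguish the two events in places: the unblinding rule in SAP 1.5.2, the COVID-19 appendix (which also labels drug discontinuation and withdrawal separately), the drug-only stop in Protocol 2.10, and the safety endpoint on stopping treatment. A reader might infer that off-drug data will not be collected and that the EASI-score and itch analyses must therefore be one analysis. The documents do not support that: the section is ambiguous rather than restrictive, some stoppers are retained, and identity holds only under the conditions in step 2 of the working. This part of the objection stands.

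It also stands that the numbers are soft. Three of the five grounds in 5.3 (withdrawn consent, sponsor termination, detention) largely rule out later visits, so fewer patients could be recovered than the number who stop. The EASI-75 gaps of 3 to 10 points at 10% to 23.3% stopping are small beside a 95% half-width of 1.96·√[(0.24 + 0.16)/30] = 0.226, about 23 points at 30 per arm.

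What does not stand is that silence is enough. The unblinding rule sits in the SAP and covers one small group, and the COVID-19 wording names no assessments. With a tenth of stoppers retained, the EASI-score pair still differs by only 0.12 to 0.40 points in the simulation, so these exceptions alone would leave the check with little content.

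**Conclusion.** The point holds as a gap between what the SAP analyses and what the protocol requires sites to collect. Off-drug EASI, IGA and diary data are not required in general and may be largely missing. If so, the two supplementary analyses of EASI score and itch would agree exactly or nearly so, and the EASI-75 treatment-policy analysis would come close to an analysis of patients still on treatment.

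A reader might go further and infer that the primary result is compromised, or that 23% of patients are expected to stop drug. Neither follows. The primary and main continuous analyses use no off-drug assessments, the 23.3% margin also serves safety data, and the EASI-75 pair stays distinct because its missing-data methods differ.

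The consequence is limited to supplementary analyses in a phase II trial. Its size depends on the unknown number of drug-only stoppers, how many are retained, and how they fare off drug. It is still worth correcting, because the remedy is cheap and later analysis cannot supply the data.

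**What to change.** Reconcile Protocol 5.3 with SAP 1.5.2 and the COVID-19 appendix, as follows.

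- **Protocol 5.3:** state that a patient who stops study drug, has not withdrawn consent, and whose continued participation the investigator does not judge to be against their interest is asked to attend the already scheduled EASI and IGA assessments and keep the diary, without injection, through Week 16. Keep the Early Termination visit for patients leaving the study.
- **SAP 2.2:** state how Early Termination assessments are assigned to a week, or that they are not. In 5.2.2, name the model for the observed-data analysis of the continuous endpoints.
- **Case report form and SAP 4.2:** record the date and reason for stopping drug separately from study withdrawal, and tabulate both.

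The criteria for stopping treatment are unchanged, as are the sample size and the primary analysis. The cost is protocol and SAP wording, one more recorded event, and some visit and diary burden for patients who stop drug. Some will decline, so the report should give the number of stoppers with a Week 16 assessment in each arm.

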### **5.4 TRIAL STOPPING RULES**

Sponsor may terminate this study prematurely, either in its entirety or at any study site, for reasonable cause provided that written notice is submitted in advance of the intended termination. The investigator may also terminate the study at his/her site for reasonable cause, after providing written notice to Sponsor in advance of the intended termination. Advance notice is not required by either party if the study is stopped due to safety concerns. If Sponsor terminates the study for safety reasons, Sponsor will immediately notify the investigator by phone and subsequently provide written instructions for study termination.

### **5.5 EMERGENCY UNBLINDING**

Subjects and investigators will be unblinded to their treatment allocation after database lock. In the event of an emergency that would require the investigator to be aware of the treatment allocation prior to the end of the trial, the investigator can obtain this information, on a per subject basis, after consultation with the Sponsor's Medical Monitor, if possible. Every effort should be made to consult with the Medical Monitor prior to emergency unblinding. Events that qualify as emergencies are as follows:

- A grade 3 or greater AE which are “probably or definitely” related to study drug, and only if **treatment assignment information is essential for the management of the event**. This type of reaction would require that the patient receives no further doses, and is followed until the resolution of the toxicity.
- Any suspected, unexpected, serious adverse reaction (SUSAR)
- Pregnancy

## **6. CORRELATIVE STUDIES**

### **6.1 PHARMACOKINETICS (PK) SAMPLE COLLECTION**

The process for the collection, storage, future use and disposal of biological samples will follow company policies and SOPs. Patient blood will be drawn into blood collection tubes at each collection time point per the study protocol for PK/ADA/PD/research analysis. These samples will be processed by the collection lab per the study laboratory manual and the obtained plasma/serum will be sent to a central laboratory before being shipped to XBiotech in monthly batches for analysis.

An enzyme-linked immunosorbent assay (ELISA) has been developed and validated to specifically measure bermekimab levels in human plasma. Blood samples will also be used to test for the presence of treatment-emergent antibodies against bermekimab. XBiotech has developed and validated an ELISA method to measure treatment-emergent ADA. Additionally, samples will be used for pharmacodynamic analysis and exploratory research.

## **7. ASSESSMENT OF SAFETY**

Safety will be assessed by monitoring adverse events, vital signs, physical examinations, ECG, and clinical laboratory measurements. Data from ECG will be included in safety analysis only when all of these measures are available for each subject (baseline and last visit). Adverse events will be monitored from visit 1 (post-injection) through visit 34 (week 36). Any serious adverse events whether related to study drug or not will be followed up until resolution.

Study drug, bermekimab, will be administered under close observation in a facility equipped to handle anaphylaxis or injection site reactions. Subjects must be closely monitored at the study site at visits 1, 2 and 3 (for the first three injections) until at least 30 minutes following the administration of the antibody. Vital signs and AE assessments will be done at 30 minutes (+/- 10 minutes) post-injection.

Any grade 3 or greater injection site reaction must be reported to the sponsor within 24 hours of learning of the event.

